### 5.3 Flowchart of the study cohort assembly

	Optum		MarketScan		Medicare*	
	Less Excluded Patients	Remaining Patients	Less Excluded Patients	Remaining Patients	Less Excluded Patients	Remaining Patients
All patients		77,673,639		200,203,908		23,466,175
Did not meet cohort entry criteria	-73,445,846	4,227,793	-196,533,760	3,670,148	-18,348,713	5,117,462
Excluded due to insufficient enrollment	-623,954	3,603,839	-340,051	3,330,097	-1,288,867	3,828,595
Excluded due to prior use of referent	-3,168,921	434,918	-2,967,886	362,211	-3,495,789	332,806
Excluded due to prior use of exposure	-29,778	405,140	-12,511	349,700	-33,013	299,793
Excluded because patient qualified in >1 exposure category	-8	405,132	-3	349,697	-9	299,784
Excluded based on Age	0	405,132	-1	349,696	0	299,784
Excluded based on Gender	-39	405,093	0	349,696	0	299,784
Excluded based on Inclusion #1 - Age >=18 years old	-624	404,469	-1,354	348,342	-721	299,063
Inclusion #3 - HFpEF prediction algorithm applied to reference group†	-381,531	22,938	-337,242	11,100	-259,816	39,247
Excluded based on Inclusion #4b - Hospitalization for HF within the last 12 months	-9,321	13,617	-4,618	6,482	-10,685	28,562
Excluded based on Inclusion #5a - ACEis or ARBs	-1,224	12,393	-385	6,097	-1,534	27,028
Excluded based on Inclusion #5b - Beta-blockers	-673	11,720	-248	5,849	-2,128	24,900
Excluded based on Exclusion #3 - Known history of angioedema	-56	11,664	-29	5,820	-200	24,700
Excluded based on Exclusion #4 - Treatment with both ACEis AND ARBs	-15	11,649	-9	5,811	-34	24,666
Excluded based on Exclusion #5 - Acute decompensated HF	-1,060	10,589	-435	5,376	-5,457	19,209
Excluded based on Exclusion #6 - Symptomatic hypotension	-734	9,855	-240	5,136	-1,964	17,245
Excluded based on Exclusion #7 - Low eGFR / renal dysfunction	-1,064	8,791	-403	4,733	-2,833	14,412
Excluded based on Exclusion #8 - Hyperkalemia	-57	8,734	-14	4,719	-116	14,296
Excluded based on Exclusion #9 - ACS, Stroke, TIA, CABG, PCI, Other CV Procedures, Carotid Angioplasty	-765	7,969	-546	4,173	-2,912	11,384
Excluded based on Exclusion #11 - Implantation of CRT device	-41	7,928	-19	4,154	-1,550	9,834
Excluded based on Exclusion #12 - History of heart transplant or LVAD	-56	7,872	-33	4,121	-35	9,799
Excluded based on Exclusion #13 - History of severe pulmonary disease	-463	7,409	-205	3,916	-1,029	8,770
Excluded based on Exclusion #14 - Diagnosis of peripartum- or chemotherapy-induced cardiomyopathy	-38	7,371	-34	3,882	-60	8,710

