3	LVEF ≤ 35%	
Measured 180 days prior to and including the day of index drug initiation in any diagnosis position and inpatient or outpatient care setting
 
Systolic Heart Failure
 
ICD-9 diagnosis: 428.2x
 
ICD-10 diagnosis: I50.2x
 
Combined Systolic/Diastolic Heart Failure
 
ICD-9 diagnosis: 428.4x
 
ICD-10 diagnosis: I50.4x
		
4	Plasma BNP ≥150 pg/mL or NT-proBNP ≥600 pg/mL at the screening visit and a hospitalization for HF within the last 12 months			
4a	Plasma BNP ≥150 pg/mL or NT-proBNP ≥600 pg/mL at the screening visit			
AND the following:				

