1	History of hypersensitivity or allergy to any of the study drugs, drugs of similar chemical classes, ACE inhibitors (ACEIs), ARBs, or neprilysin inhibitors, as well as known or suspected contraindications to the study drugs		
2	Previous history of intolerance to recommended target doses of ACEIs or ARBs		
3	Known history of angioedema	
Measured from the start of all available data to index drug initiation in any diagnosis position and inpatient or outpatient care setting
 
ICD-9 diagnosis: 995.1 ICD-10 diagnosis: T78.3x
	
4	Requirement for treatment with both ACEIs and ARBs	
Measured 180 days prior to and including day of drug initiation in prescription claims (generic names) for any of oral ACEi and ARB for two subsequent dispensings
 
ACE inhibitors' generic names for prescription claims: Enalapril, Captopril, Clazapril, Fosinopril, Lisinopril, Moexipril, Perindopril, Quinapril, Ramipril, Trandolapril, Zofenopril, Benazepril
 
-AND-
 
ARBs generic names for prescription claims: Candesartan, Eprosartan, Irbesartan, Losartan, Olmesartan, Telmisartan, Valsartan, Azilsartan
	
5	Current acute decompensated heart failure (exacerbation of chronic heart failure manifested by signs and symptoms that may require intravenous therapy)	
Measured 7 days prior to and including day of drug initiation in any diagnosis position and inpatient and emergency care setting
 
ICD-9 diagnosis: 428.41, 428.43 ICD-10 diagnosis: I50.23, I50.41, I50.43
	
6	Symptomatic hypotension and/or a systolic blood pressure <100 mmHg at Visit 1 (screening) or <95 mmHg at Visit 3 or at Visit 5 (randomization)	
Measured 30 days prior to and including day of drug initiation in any diagnosis position and inpatient or outpatient care setting
 
Hypotension: ICD-9 diagnosis: 458.xx, 785.5x ICD-10 diagnosis: I95.xx, R57.xx
	

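### The code list for Exclusion 5 (current acute decompensated HF) is inconsistent: it has I50.23 but not 428.23, and acute combined codes but not acute systolic codes (428.21, I50.21)

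*Protocol*

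**What the plan says.** Appendix A, Exclusion 5, takes over the trial criterion as "Current acute decompensated heart failure (exacerbation of chronic heart failure manifested by signs and symptoms that may require intravenous therapy". That wording does not restrict the criterion to one type of heart failure. The claims version uses this window and setting: "Measured 7 days prior to and including day of drug initiation in any diagnosis position and inpatient and emergency care setting". The codes are printed in full: "ICD-9 diagnosis: 428.41, 428.43 ICD-10 diagnosis: I50.23, I50.41, I50.43".

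Appendix A, Inclusion 3, qualifies patients on either of two code families. Systolic HF is "ICD-9 diagnosis: 428.2x" and "ICD-10 diagnosis: I50.2x". The other family, "Combined Systolic/Diastolic Heart Failure", is 428.4x and I50.4x. In the flowchart the row for this criterion reads "Inclusion #3 - HFpEF prediction algorithm applied to reference group", so the code families alone do not describe how it was run.

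The flowchart in Section 5.3 reports the effect of the exclusion in the row "Excluded based on Exclusion #5 - Acute decompensated HF": 1,060 patients removed in Optum, 435 in MarketScan and 5,457 in Medicare.

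**The concern.** An exclusion for a clinical state should not turn on which of several equivalent codes was recorded. Here it does. The list covers combined HF fully in both code systems. It covers systolic HF with a single ICD-10 code and no ICD-9 code, yet systolic HF is one of the two groups through which patients qualify.

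The rest of Appendix A treats the omitted codes differently. The primary outcome and Inclusion 4b both take 428.x and I50.2x. An inpatient claim with I50.21 therefore counts as an HF admission for entry and as an outcome event, but not as decompensation for Exclusion 5.

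At stake is who is eligible at a large step of cohort assembly, in a study whose primary composite includes HF hospitalization. Power is hardly affected.

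**Working it through.** **1. Reproduce the flowchart row.** Each remaining count equals the previous count minus those removed (Section 5.3).

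| Database | Before | Removed | After (computed = printed) | Share removed |
|---|---|---|---|---|
| Optum | 11,649 | 1,060 | 10,589 | 9.1% |
| MarketScan | 5,811 | 435 | 5,376 | 7.5% |
| Medicare | 24,666 | 5,457 | 19,209 | 22.1% |
| Sum | 42,126 | 6,952 | 35,174 | 16.5% |

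In total this is the largest of the numbered exclusions. The next is Exclusion 7, with 1,064 + 403 + 2,833 = 4,300. Medicare supplies 5,457 / 6,952 = 78% of the removals.

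**2. Compare the code sets.** I expanded the four families of Inclusion 3 and kept the codes ending in 1 (acute) or 3 (acute on chronic). The meaning of the last digit is ICD convention; the protocol does not spell it out.

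| HF type | Acuity | ICD-9 | Listed? | ICD-10 | Listed? |
|---|---|---|---|---|---|
| Systolic | acute | 428.21 | no | I50.21 | no |
| Systolic | acute on chronic | 428.23 | no | I50.23 | yes |
| Combined | acute | 428.41 | yes | I50.41 | yes |
| Combined | acute on chronic | 428.43 | yes | I50.43 | yes |

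Five of eight are listed. The missing three are 428.21, 428.23 and I50.21. There are two separate inconsistencies:
- Between code systems: row 2 has the ICD-10 code without its ICD-9 counterpart.
- Between HF types: row 1 is empty while row 3 is full.

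**3. Apply the list as written.** Take a patient with an inpatient claim three days before index.
- Claim carries I50.21 and no listed code: kept.
- Same claim with I50.41, I50.43 or I50.23: removed.
- Same state recorded as 428.23 in the ICD-9 period: kept, unless 428.41 or 428.43 also appears in any position.

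**4. Bound the weight of the ICD-9 part.** Entry opens on 7 July 2015 in all three databases (Section 5.2.1). In Appendix B after matching, initiators in 2015–2016 number 146 + 153 (Optum), 229 + 233 (MarketScan) and 355 + 374 (Medicare), which is 1,490 of 6,066 (24.6%). The protocol does not give the date on which coding changed. On the assumption that ICD-9 claims fall only in the early part of that band, the share exposed to the 428.2x gap is smaller than 24.6%, and I50.21 carries most of the practical weight.

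**5. Price the repair in power.** Power = Φ(½·√D·|ln HR| − 1.96). With the plan's D = 1,305.7 and HR = 0.8, ½ × 36.13 × 0.2231 − 1.96 = 2.07, so power is 0.981, as printed in the Final Power Assessment. For assumed losses of expected pooled events:

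| Events lost | Pooled power |
|---|---|
| 1% | 0.980 |
| 5% | 0.976 |
| 10% | 0.969 |
| 20% | 0.950 |

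**The case against.** **The acute systolic codes may be left out on purpose.** The criterion speaks of an exacerbation of chronic HF. That fits acute-on-chronic codes best, and I50.21 or 428.21 could be read as new-onset disease. Inclusions 5a and 5b, which require 28 days of an ACEi or ARB and of a beta-blocker, point to established disease. This has force: 428.23 is the clearest omission. But that reading cannot explain why 428.41 and I50.41 are listed, nor why 428.23 is not. It would be a second way to make the HF types consistent (drop the acute combined codes), and the protocol does not choose it.

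**The implemented list may differ.** Appendix A says full ICD-10 lists sit in an external folder. For Exclusion 5, however, the ICD-10 codes are printed with no pointer to a tab, unlike Exclusions 9 and 11, and the remark does not concern ICD-9.

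**Stronger readings that a reader might infer, and that the protocol does not support:**
- *Acutely decompensated systolic patients are admitted in general.* They are not. I50.23 is listed, and codes count in any position, so a patient with any listed code is still removed.
- *The leak runs to hundreds or more.* Taking 5–20% of 6,952 gives 348–1,390, but the protocol gives no basis for those percentages, and later exclusions and matching would cut the number.
- *The leak biases the comparison in a known direction.* One list applies to both arms and nothing is reported by arm. HF hospitalization is balanced after matching (81.4% vs 82.2%, 80.5% vs 79.3% and 73.9% vs 73.6% in Optum, MarketScan and Medicare). Time since the last admission is not among the covariates visible, but the Appendix B table is cut off, so its absence cannot be asserted.
- *Leaked patients add events in the first days.* Section 6.3.2 starts follow-up the day after initiation, but Appendix A measures the primary outcome 14 days after it. If that is a lag, the first two weeks do not count.
- *The cohort is defined by systolic HF alone.* It is systolic or combined HF, with a prediction algorithm applied to the reference group.

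**Conclusion.** The point holds as an inconsistency and incompleteness in the printed code list. Exclusion 5 lacks three of the eight acute-type codes in the families that qualify patients: 428.23 against the listed I50.23, and 428.21 and I50.21 against the listed 428.41 and I50.41. Eligibility at a step that removed 16.5% of the patients reaching it (7.5% to 22.1% by database) therefore depends partly on code choice.

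The number of patients affected and any difference between arms are unknown, so no claim of bias in the hazard ratio follows. The conclusion rests on the ICD meaning of the last digit and on the list having been run as printed. It is firmest for 428.23, which matters only for early entrants. It is less firm for I50.21, which has more practical weight.

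**What to change.** - Add 428.23, so that the ICD-9 and ICD-10 halves of Exclusion 5 match.
- Treat acute codes alike for systolic and combined HF by adding 428.21 and I50.21, in line with the listed 428.41 and I50.41. If the sponsor means acute-on-chronic HF only, the protocol should say so and explain the acute combined codes.
- Check the printed list against the external code folder and state which was run.
- Rerun the 7-day step and report the additional exclusions by arm and database. Then update matching, balance and power before the outcome analysis. The protocol already pauses at that stage for review of balance and final power.

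The cost is a code-list edit, a cohort rerun, some loss of patients and slightly lower stated power: pooled power stays near 0.97 even if 10% of expected events were lost. If few patients are added and they split evenly between arms, the report closes the matter.

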# Appendix A

7	
Estimated glomerular filtration rate (eGFR) <30 mL/min/1.73 m^2 at Visit 1 (screening), Visit 3 (end of enalapril run-in), or Visit 5 (end of LCZ696 run-in and randomization) or >35% decline in eGFR between Visit 1 and Visit 3 or between Visit 1 and Visit 5
 
Measured 30 days prior to and including day of drug initiation in any diagnosis position and inpatient or outpatient care setting
 
Acute kidney injury (AKI) ICD-9 diagnosis: 584.xx, 586 ICD-10 diagnosis: N17.x, N19
 
Acute glomerulonephritis ICD-9 diagnosis: 580.xx ICD-10 diagnosis: N00.3, N00.8, N00.9, N01.3
 
Chronic Kidney Disease (CKD) - Stage IV and V ICD-9 diagnosis: 585.4, 585.5 ICD-10 diagnosis: N18.4, N18.5
 
ESRD ICD-9 diagnosis: 403.01, 403.11, 403.91, 404.03, 404.13, 585.6 ICD-10 diagnosis: N12.0, N18.6
 
Hemodialysis/Peritoneal Dialysis ICD-9 diagnosis: V45.1x, V56.xx, 996.56, 996.68, 996.73 ICD-10 diagnosis: Z49.xx, Z91.15, Z99.2, T85.611x, T85.631x, T85.691x, T85.71x ICD-9 procedure: 39.95, 54.98 ICD-10 procedure: 5A1D70Z, 5A1D80Z, 5A1D90Z, 3E1M39Z CPT-4 code: 90935, 90937, 90939
	
8	
Serum potassium >5.2 mmol/L at Visit 1 (screening) or >5.4 mmol/L at Visit 3 or Visit 5 (randomization)
 
Measured 30 days prior to and including day of drug initiation in any diagnosis position and inpatient or outpatient care setting
 
Hyperkalemia ICD-9 diagnosis: 276.7 ICD-10 diagnosis: E87.5
	
9	
Acute coronary syndrome, stroke, transient ischaemic attack, cardiac, carotid, or other major cardiovascular surgery, PCI, or carotid angioplasty within the 3 months prior to Visit 1.
 
Measured 90 days prior to and including day of drug initiation in any diagnosis position and inpatient or outpatient care setting
 
Acute Coronary Syndrome: STEMI & NSTEMI ICD-9 diagnosis: 410.xx (exclude 410.x2), 411.0 ICD-10 diagnosis: I21.xx, I22.xx, I23.xx
 
Acute Coronary Syndrome: Unstable Angina ICD-9 diagnosis: 413.xx (exclude 413.1), 411.1, 411.8, 411.81, 411.89 ICD-10 diagnosis: I20.xx (exclude I20.1), I24.xx (exclude I24.1)
 
Stroke ICD-9 diagnosis: 430.xx, 431.xx, 433.x1, 434.xx (excluding 434.x0), 436.x, 997.02 ICD-10 diagnosis: G97.3x, I60.xx, I61.xx, I62.xx, I63.xx, I67.89, I97.81x, I97.82x
 
TIA ICD-9 diagnosis: 435.xx ICD-10 diagnosis: G45.xx
 
CABG / Transmyocardial Revascularization ICD-9 diagnosis: V45.81, 996.03 ICD-10 diagnosis: Z95.1 ICD-9 procedure: 36.1x, 36.2, 36.3x ICD-10 procedure: Refer to "CABG & Revascularization" tab within this spreadsheet for complete list of procedure codes
	
10	
Coronary or carotid artery disease likely to require surgical or percutaneous intervention within the 6 months after Visit 1
 
Included above
	
11	
Implantation of a cardiac resynchronization therapy (CRT) device within 3 months prior to Visit 1 or intent to implant a CRT
 
Measured 90 days prior to and including day of drug initiation in any diagnosis position and inpatient or outpatient care setting
 
Pacemaker and Implantable cardiac Defibrillators: ICD-9 diagnosis: V45.01, V45.02, V45.09, V53.31, V53.32, 996.01, 996.04, 996.61 ICD-10 diagnosis: Z95.0, Z95.810, Z45.010, Z45.018, Z45.02, T82.110A, T82.111A, T82.120A, T82.121A, T82.190A, T82.191A, T82.6XXA, T82.7XXA ICD-9 procedure: 00.50, 00.51, 00.53, 00.54, 37.7x, 37.8x, 37.94 - 37.98 ICD-10 procedure: Refer to "CRT_Implant" tab CPT-4 code: 33200 - 33208, 33220 - 33229, 33230 - 33238, 33240 - 33249, 33262 - 33264, 33270, 33271, 93640 - 93642, 93280 - 93289, 93290 - 93299
	

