8	Number of hospitalizations for CHF	ICD-9 diagnosis: 428.x, 398.91, 402.01, 402.11, 402.91, 404.01, 404.11, 404.91, 404.03, 404.13, 404.93 ICD-10 diagnosis: I50.1, I50.2x, I50.4, I50.814, I09.81, I11.0, I13.0, I13.2	0.346289	Measured 180 days prior to and including the date of index drug initiation	6 months prior to index date (including index date)
9	Male gender	Male	0.323651	Measured on the date of index drug initiation	on index date
10	Implantable cardioverter defibrillator	ICD-9 diagnosis: V45.02 ICD-10 diagnosis: Z95.810 ICD-9 procedure: 37.94 - 37.98 ICD-10 procedure: Please copy from ICD-10 codes tabs for implantable cardioverter defibrillator	0.275032	Measured 180 days prior to and including the date of index drug initiation	6 months prior to index date + index date + 30days post-index

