30	Depression	ICD-9 diagnosis: 293.83, 296.2x, 296.3x, 296.9x, 298.0x, 300.4x, 309.1x, 309.28, 311.xx ICD-10 diagnosis: F06.3x, F32.x, F33.x, F34.x, F39.x, F43.21, F43.23	-0.033829	Measured 180 days prior to and including the date of index drug initiation	6 months prior to index date + index date + 30days post-index
31	Hypotension	ICD-9 diagnosis: 458.xx ICD-10 diagnosis: I95.x	-0.017282	Measured 180 days prior to and including the date of index drug initiation	6 months prior to index date + index date + 30days post-index
32	Stable angina	ICD-9 diagnosis: 413.xx ICD-10 diagnosis: Please copy from ICD-10 tab for stable angina	-0.015657	Measured 180 days prior to and including the date of index drug initiation	6 months prior to index date + index date + 30days post-index
33	Age	Continous	-0.005747	Measured on the date of index drug initiation	on index date

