## Appendix A

Trial ID	pNDA32
Trial Name (with web links)	PARADIGM-HF
Trial Name (with pdf links)	PARADIGM-HF
NCT	NCT01035255
Trial category	Primary indication
Therapeutic Area	Cardiology/Vascular Diseases
Study batch	Heart failure medications
RCT Category	1a- Intended S with label change
Brand Name	Entresto
Generic Name	SacubitriI/valsartan
Sponsor	Novartis
Year	2015
Measurable endpoint	Composite endpoint including death from cardiovascular causes or and hospitalization for heart failure
Exposure	LCZ696 200 mg
Comparator	Enalapril 10 mg
Population	80% Diuretic, 29% Digitalis, 93% $\beta$ blocker, 54% Mineralocorticoid antagonists, 15% ICD & 7% CRT users
Trial finding	HR = 0.80 (95% CI 0.73– 0.87)
Notes	
No. of Patients	8442
Non-inferiority margin	-
Assay Sens. Outcome	
Assay Sens. Endpoint (from trial)	
Finding for potential Assay Sens. Outcome from trial-	
Power	
Blinding	Double-blinded
Statistical Method	
Approval indication	To reduce the risk of CV death and hospitalization for heart failure in patient swith chronic heart failure (NYHA class II-IV) and reduced rejection fraction

[figure not shown]
[figure not shown]
[figure not shown]

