Calendar Time - Year of Initiation (2015/16 - 2020)	...2015-2016; n (%)	146 (11.4%)	153 (12.0%)	-0.0187	229 (30.6%)	233 (31.1%)	-0.0108	355 (35.3%)	374 (37.2%)	-0.0395	797 (26.3%)	785 (25.9%)	0.0091
...2017; n (%)	293 (22.9%)	280 (21.9%)	0.0240	264 (35.3%)	256 (34.2%)	0.0231	651 (64.7%)	632 (62.8%)	0.0395	293 (9.7%)	280 (9.2%)	0.0171	
...2018; n (%)	321 (25.1%)	319 (24.9%)	0.0046	255 (34.1%)	259 (34.6%)	-0.0105	0 (0.0%)	0 (0.0%)	#DIV/0!	321 (10.6%)	319 (10.5%)	0.0033	
...2019 - 2020; n (%)	519 (40.6%)	527 (41.2%)	-0.0122	0 (0.0%)	0 (0.0%)	#DIV/0!	0 (0.0%)	0 (0.0%)	#DIV/0!	519 (40.6%)	527 (41.2%)	-0.0122	
Combined comorbidity score, 180 days	...mean (sd)	5.30 (2.47)	5.27 (2.43)	0.0122	4.24 (2.12)	4.19 (2.06)	0.0239	4.77 (2.49)	4.76 (2.40)	0.0041	4.86 (2.40)	4.83 (2.33)	0.0127
...median [IQR]	5.00 [4.00, 7.00]	5.00 [3.00, 7.00]	0.0000	4.00 [3.00, 6.00]	4.00 [3.00, 5.00]	0.0000	4.00 [3.00, 6.00]	4.00 [3.00, 6.00]	0.0000	4.42 (2.40)	4.42 (2.33)	0.0000	
CV Comorbidity - Pulmonary hypertension/Other pulmonary heart disease; n (%)	250 (19.5%)	257 (20.1%)	-0.0151	132 (17.6%)	126 (16.8%)	0.0212	209 (20.8%)	223 (22.2%)	-0.0341	459 (15.1%)	480 (15.8%)	-0.0194	
CV Comorbidity - Other dysrhythmias; n (%)	735 (57.5%)	736 (57.5%)	0.0000	424 (56.7%)	409 (54.7%)	0.0403	506 (50.3%)	519 (51.6%)	-0.0260	1,241 (40.9%)	1,255 (41.4%)	-0.0102	
CV Comorbidity - Valve disorder; n (%)	254 (19.9%)	237 (18.5%)	0.0356	46 (6.1%)	49 (6.6%)	-0.0205	202 (20.1%)	203 (20.2%)	-0.0025	456 (15.0%)	440 (14.5%)	0.0141	
CV Comorbidity - Hospitalization for heart failure; n (%)	1,041 (81.4%)	1,051 (82.2%)	-0.0207	602 (80.5%)	593 (79.3%)	0.0299	743 (73.9%)	740 (73.6%)	0.0068	1,784 (58.8%)	1,791 (59.1%)	-0.0061	
CV Comorbidity - Implantable cardioverter defibrillator; n (%)	328 (25.6%)	303 (23.7%)	0.0441	170 (22.7%)	170 (22.7%)	0.0000	137 (13.6%)	145 (14.4%)	-0.0231	465 (15.3%)	448 (14.8%)	0.0140	
CV Comorbidity - Hypertension; n (%)	167 (13.1%)	169 (13.2%)	-0.0030	67 (9.0%)	73 (9.8%)	-0.0274	160 (15.9%)	150 (14.9%)	0.0277	327 (10.8%)	319 (10.5%)	0.0097	
CV Comorbidity - Hypertension; n (%)	1,206 (94.9%)	1,208 (94.4%)	-0.0043	666 (88.0%)	658 (88.0%)	0.0313	972 (96.6%)	960 (95.4%)	0.0613	2,178 (71.5%)	2,168 (71.5%)	0.0067	
CV Comorbidity - Coronary atherosclerosis and other forms of chronic ischemic heart disease; n (%)	959 (75.0%)	946 (74.0%)	0.0229	436 (58.3%)	427 (57.1%)	0.0243	780 (77.5%)	788 (78.2%)	-0.0193	1,739 (52.3%)	1,724 (52.2%)	0.0020	

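### Exclusion 11 targets recent CRT implantation, but its code list captures any recorded pacemaker or defibrillator, and its yield of 0.5%, 0.5% and 13.6% across the three databases needs explaining

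*Protocol*

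**What the plan says.** Appendix A gives the trial criterion for Exclusion 11 as "Implantation of a cardiac resynchronization therapy (CRT) device within 3 months prior to Visit 1 or intent to implant a CRT". The claims implementation beside it is headed "Pacemaker and Implantable cardiac Defibrillators". It looks back 90 days up to and including the day of initiation, in any diagnosis position, inpatient or outpatient. The diagnosis codes include V45.01, V45.02, V53.31, V53.32, Z95.0, Z95.810 and Z45.02, plus complication codes such as 996.04 and T82.110A. The procedure and CPT codes are general pacemaker and defibrillator ranges. The ICD-10 procedure codes sit in a tab that is not reproduced. One definition is given for all three databases.

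Row 10 of the ejection-fraction algorithm in Appendix A uses V45.02, Z95.810 and 37.94-37.98 to mark "Implantable cardioverter defibrillator", that is, having the device. The trial summary sheet at the end of Appendix A describes the RCT population as including "15% ICD & 7% CRT users".

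The Section 5.3 flowchart row "Excluded based on Exclusion #11 - Implantation of CRT device" removes 41 patients in Optum, 19 in MarketScan and 1,550 in Medicare.

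Two other exclusions have a similar problem:
- **Exclusion 9** puts ICD-9 codes "413.xx (exclude 413.1), 411.1, 411.8, 411.81, 411.89", and all of I20.xx except I20.1, under unstable angina. Row 32 of the algorithm uses 413.xx for "Stable angina".
- **Exclusion 16** states a criterion limited to patients who have no pacemaker, but its code definition for second- and third-degree AV block carries no pacemaker condition.

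**The concern.** A status or device-check code shows that a patient has a device. It does not show that a CRT device was implanted recently. A patient whose defibrillator is years old and who has a routine check in the 90 days before index meets Exclusion 11 as coded. The RCT enrolled such patients, and Section 5.2.2 says that the criteria follow the trial as closely as the data allow.

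The flowchart adds a second question. One written rule removes almost nobody in two databases and about one patient in seven in the third. If different lists were run, the Medicare cohort is defined differently from the other two, yet the three are pooled in the power assessments and in the pooled columns of Appendix B. A reader could not then say which eligibility rule the pooled result reflects.

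**Working it through.** **1. Reproduce the flowchart row.** The number at risk is the count remaining after Exclusion 9.

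| Database | At risk | Removed | Remaining | Removed / at risk |
|---|---|---|---|---|
| Optum | 7,969 | 41 | 7,928 | 0.51% |
| MarketScan | 4,173 | 19 | 4,154 | 0.46% |
| Medicare | 11,384 | 1,550 | 9,834 | 13.62% |

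The subtractions are exact. The Medicare rate is 26.5 times Optum's and 29.9 times MarketScan's.

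**2. Compare with neighbouring steps** (Optum / MarketScan / Medicare):
- Exclusion 5: 1,060/11,649, 435/5,811, 5,457/24,666 = 9.1% / 7.5% / 22.1%
- Exclusion 7: 1,064/9,855, 403/5,136, 2,833/17,245 = 10.8% / 7.8% / 16.4%
- Exclusion 9: 765/8,734, 546/4,719, 2,912/14,296 = 8.8% / 11.6% / 20.4%

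Medicare loses more at each of these steps, but the largest ratio in a row is between about 2 and 3.

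**3. Device flags still present in Appendix B, before matching, arms combined.**
- "CV Comorbidity - Implantable cardioverter defibrillator; n" row: Optum (4,746 + 641)/19,668 = 27.4%; MarketScan (2,170 + 319)/12,010 = 20.7%; Medicare (2,292 + 249)/19,961 = 12.7%.
- CRT-device row: Optum (6,249 + 845)/19,668 = 36.1%; MarketScan (3,356 + 457)/12,010 = 31.7%; Medicare (3,595 + 357)/19,961 = 19.8%.

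The CRT-device flag is commoner than the ICD flag in every database, which fits a broad device list better than recent CRT implants. Suppose that the Appendix B patients passed Exclusion 11, and that the ICD covariate uses the row 10 codes over 180 days; neither is stated. A retained ICD flag could then come almost only from codes dated 91 to 180 days before index, because the row 10 codes shown are all in the Exclusion 11 list. It is hard to see how about 27% of Optum patients could have such a code then while only 0.5% had any listed code in the last 90 days.

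**4. Cohort sizes.** The flowchart ends at 6,946 + 3,694 + 8,031 = 18,671. Appendix B before matching has 46,268 + 5,371 = 51,639. Step 3 is therefore indirect evidence.

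**5. Size of the difference, as an illustration.** The Optum and MarketScan rate is (41 + 19)/(7,969 + 4,173) = 60/12,142 = 0.49%. Applied to Medicare, it removes 0.0049 x 11,384, or about 56, instead of 1,550. About 1,490 more patients pass this step. If the later exclusions keep the same share (8,031/9,834 = 0.817), about 1,220 more reach the final Medicare cohort, giving about 9,250 instead of 8,031.

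**6. Related rules.** Exclusion 16 removes 73 + 29 + 73 = 175 patients; the number with a pacemaker is not shown. The number removed by the angina codes within Exclusion 9 is not shown either.

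**The case against.** The strongest reply concerns the evidence for unequal application. Appendix B describes patients after exclusions. If Medicare alone lost 13.6% for device codes, fewer flags there afterwards are to be expected. Adding the removed share back, and assuming the Appendix B patients went through the same step, gives 0.136 + 0.864 x 19.8% = 30.7% for Medicare, against about 32% for MarketScan and 36% for Optum. So a reader who infers from the prevalence ordering that one list cannot have been used goes too far: the ordering is partly a product of the exclusion, and it comes from a different, larger cohort. This part of the objection stands. It does not explain why the same written list yields 0.5% where about a third of retained patients carry a CRT-device flag.

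It can also be said that device carriers are not missing from the matched data. After matching, the ICD flag is 25.6% and 23.7% in Optum, 22.7% in both arms of MarketScan, and 13.6% and 14.4% in Medicare, against 15% in the RCT. That is fair. Loss of carriers is visible in the flowchart mainly for Medicare.

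Part of the code list is in a tab not shown, and the colour grading of mapping quality did not survive the PDF reading, so the sponsor may already rate this row as imperfect. The diagnosis and CPT codes on the page are enough to show that the list is too broad.

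On Exclusion 16, a reader might infer that every AV-block patient is removed. The definition covers second- and third-degree block and leaves out 426.11, and Exclusion 11 as written would already have removed some pacemaker carriers.

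**Conclusion.** The point holds in two parts of different strength. That the Exclusion 11 list is broader than its criterion is plain from Appendix A: it excludes patients with a device code recorded in the 90-day window (not every carrier), whatever the implant date, and the RCT enrolled device users. That the list was not run alike is a strong inference from yields of 0.51%, 0.46% and 13.6%. The protocol does not state it, and the documents do not show which execution was intended.

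Two further readings are not supported. A biased hazard ratio cannot be derived, because the flowchart does not split exclusions by arm. Nor is this a power problem: the correction keeps device carriers in the cohort rather than removing them.

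The illustrative gain of about 1,490 Medicare patients at this step, or 1,220 in the final cohort, assumes that the Optum and MarketScan rate applies and that later steps remove unchanged proportions. The faults in Exclusions 9 and 16 are real but smaller, and the numbers affected cannot be sized from the protocol.

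**What to change.** - Restrict Exclusion 11 to CRT implantation procedure codes in the prior 90 days. Drop the status, check and complication codes, or justify the wider list.
- Check the unlabelled CPT table in Appendix A, which includes 33200-33249 and 33250-33275. If it belongs to Exclusion 9, it may remove the same device patients there, and narrowing Exclusion 11 alone would not bring them back.
- Run one identical list in all three databases, and explain any large difference in yield that remains.
- Keep ICD and pacemaker carriage as a propensity-score covariate.
- Remove 413.xx and the ICD-10 codes for stable angina from the acute coronary syndrome part of Exclusion 9.
- Align Exclusion 16 with its stated criterion by adding the no-pacemaker condition.
- Re-run the flowchart and reconcile its 18,671 patients with the 51,639 in Appendix B.

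The cost is edits to three code lists and a re-run of cohort assembly, matching and the balance tables. No new data are needed.
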